2. RESEARCH PLAN

Purpose of Study:
The primary aim of this study is to see if the use of an antiseptic preparation (povidone iodine) versus cold normal saline, will decrease rates of urine contamination during the non-invasive Quick Wee (QW) collection of pediatric urine.
Hypotheses, Research Questions, or Objectives:
To evaluate two different cleansing solutions in controlling urine contamination.
Significance
If the use of antiseptic preparation decreases the level of contamination in this study then it would provide an effective and reliable clean catch method that staff could utilize prior to electing for catheterization or suprapubic aspiration.
Military Relevance:
Having a noninvasive Quick Wee method with a high 5 minute void success rate; patient wait times in the emergency department will decrease, and parents will be happier with avoiding invasive measures. This improves patient safety, and provides the clinician with another method for collecting urine. In the Air Force's move towards a culture of safety, and zero harm; further evaluation into this novel technique's reliability will support our goals provided rates of urine contamination can be minimized. The importance of researching noninvasive methods with low levels of contamination is that it may prevent further invasive methods from being used. For example if a child's urine specimen from clean catch is contaminated the next step would be to get the sample via catheterization, a method that is traumatic to child, parent and sometimes staff. If research shows that urogenital prep with iodine decreases level of contamination in the urine then it provides an acceptable method of urine clean catch collection.
Background and Review of Literature:
Urinary tract infections (UTI) are common acute illnesses among pediatric patients, accounting for 5-7% of emergency department visits in the under two-year-old population [1]. However, obtaining urine samples from the precontinent patient can be difficult. There is an ongoing debate regarding which noninvasive method for urine specimen collection is best for this population. The main argument against clean catch is the high rate of contamination compared to invasive collection and reliability.
There are many methods of noninvasive urine collection. These methods are preferred as they are fairly well tolerated by patients, less distressing to parents, cost effective, and require less technical expertise. In the past; these methods have been dismissed due to their high rates of contamination, time to void and also effectiveness. The National Institute of Health and Clinical Excellence (NICE, UK) recommends a clean-catch urine (CCU) be the first attempt at obtaining a urine specimen from children suspected of having UTI [2]. This means placing the urine specimen collection container into the urine mid-stream once the child has begun to void to avoid contamination. Conversely, the American Academy of Pediatrics recommends clean

catch urine for screening and a catheter specimen urine collection or suprapubic aspiration for definitive diagnosis [3]. Both of these invasive techniques produce quick urine samples with low rates of contamination; however they can be painful and distressing to both the patient and parent.

The Quick-Wee method for noninvasive urine collection has been evaluated in a one randomized controlled trial and has been shown to significantly increase the five minute voiding success rate for CC urine collection; 31%, n= 174. However a past study demonstrated contamination rate of 27%, n=174. No study has directly evaluated the use of antiseptic solution in the evaluation of the QW rate of contamination in pediatric patients. The purpose of this study is to see whether the use of povidone iodine swabs prior to the QW method will decrease the rate of contamination. A decrease of the rate of contamination would strengthen the validity of this simple CCU method. Also using the this method for the collection method in both the experimental and control groups will further evaluated the five min void success rate.

We chose to use iodine as our prepping agent because it is currently the standard cleaning solution used for adult and pediatric patients. It is readily available, inexpensive and has been shown to be less caustic then other prepping agents.

Bibliography:

1. Shaw, K. N., Gorelick, M., McGowan, K. L., Yakscoe, N. M., & Schwartz, J. S. (1998). Prevalence of urinary tract infection in febrile young children in the emergency department. *Pediatrics*, *102*(2), e16-e16.

3. RESEARCH DESIGN AND METHODS

Research Design and Methods:

Male and Female DoD beneficiaries, aged one month (28 days) to 12 months (365 days), meeting the inclusion/exclusion criteria will be offered an opportunity to participate. Each child will already be scheduled for a standard of care urinalysis collection procedure through their pediatric PCM. They will be recruited from the clinics located at the 99MDG through direct contact with the infant’s parents. All of the below items are research-related unless marked as ‘standard of care’:

The study will be a non-blinded randomized controlled trial with parallel assignment of groups, taking place in the pediatric and emergency departments. The subject’s parents will be asked if the patient has had an allergic reaction to iodine in the past prior to being placed in experimental group and if they have had a reaction in the past they will be placed in the normal saline group instead. Additionally, if the patient develops a reaction to iodine during testing then they will have the region cleansed with normal saline, will be evaluated by the medical staff performing the test, then the urine and subject’s data will be disposed of and excluded from the study. The experimental group will have their periurethral region cleansed with povidone iodine solution while the control group will be prepped with cold (2°C) normal saline. Both groups will have the urine collection performed utilizing the QW method (see attached flow chart). If a sample is not collected within five minutes with the QW method it will be documented as a failure and the child will be referred back to their pediatric PCM and removed from the study. Urine collection will occur at the hospital.

Utilizing sequentially numbered opaque sealed envelopes (SNOSE), children will be randomly assigned to one of the two treatment groups. The envelopes will contain plastic forceps, gauze, and a 3x5 index card listing the group the child has been assigned, i.e., iodine or normal saline, as well as child’s ID number; For the experimental group there will be a package of iodine swabs and the control will have a normal saline flush. Also contained within the envelope will be the Participant Data Sheet to provide an easy way to track the urine collection process for the study..

Children will then have their periurethral region gently cleansed for ten seconds with one of the previously discussed solutions. The procedure requires cold saline (approximately 2°C) soaked gauze to be applied in a circular motion over the bare suprapubic region of the child continuously for five minutes. The saline will come in the form of sterile saline flushes kept in a cooler of ice in the departments were the study is being conducted.

If the child voids within five minutes the time in seconds will be recorded on the provided worksheet. Also whether or not the urine was successfully “caught” in the specimen cup will be documented. Whether or not the sample was contaminated by lab standards will also be recorded on the data sheet once the results are available.

At the conclusion of the child's participation, the parents will be asked to complete a Satisfaction Survey asking their overall satisfaction with the collection method utilized.						
a. Interventions and Observations:						
The primary outcome of this study is to evaluate whether there is an improvement in the rate of urine contamination with iodine solution over normal saline prior to the QW. The secondary outcome will be the QW's rate of success in providing a CCU in five minutes.						
b. Setting:						
This study will be conducted at the 99MDG at Nellis AFB. Children will be recruited from the emergency department as well as the pediatric clinic through parental permission and consent. Research Staff will enroll children through parental authorization, based on the child's age, and if a standard of care urinalysis will be needed during their course of treatment, based on the determination of the child's attending physician. If a urinalysis is not needed as a course of treatment for the infant, the child will not be accepted for the study.						
c. Date(s):						
11 January 2019 – 31 May 2019						
d. Subjects:						
The sample population for this study are DoD beneficiary children from 28 days of age to 12 months requiring a standard of care urinalysis procedure as a course of treatment. They will be patients enrolled at 99MDG for evaluation and treatment. Children will be recruited from the pediatric clinic as well as the emergency department through parental permission and consent.						
e. Inclusion/Exclusion Criteria:						
Inclusion Criteria	
 DoD children aged one month (28 days) to 12 months (365 days) if the child was born less than 36 weeks gestation, age will be corrected Precontinent (meaning that the child is unable to void on command) Treating clinician has determined that the child requires urine sample collection for course of treatment. 					
Exclusion Criteria	
 Children that are outside of the age range discussed in the inclusion criteria (less than one month (28 days) and older than 12 months (365 days)). If the treating clinician has determined that there is a need for immediate treatment and urine sample collection via invasive method, any type of anatomical or neurologic condition that will affect the ability to void or sensation of the suprapubic area. Children with past hypersensitivity reactions to iodine swabs. 					
f. Source of Research Material:						
Will you be using private information in this study?				 Yes		
If Yes		 protected health information (PHI) held by a covered entity				
Use of identifiers with private information						
Identifiers to be Used?	Column A Looked at by research team	Column B Recorded on enrollment log, subject list, or key list	Column C Recorded on data collection tool (survey, spreadsheet, etc.)	Column D Recorded on specimen containers	Column E Shared w/ others not on research team	Column F Stored after study ended
Names						
Study codes linked to individuals' identities using a key only accessible by the researcher						
Dates (except year)						
Phone/Fax Numbers						
DoD ID# & FMP code						
Coding Plan?						
Describe the method that will be used		Each participant will be assigned a patient identifier starting with either A or B to				

to create and assign unique study codes to data.	show which group they were a member of and number 01-60 following the letter.		
Describe the method that will be used to create and assign unique study codes to specimens.	Urine specimens will be associated with the child's DoD ID# and FMP code for the initial results from the hospital laboratory and then the microscopy results will be put into the work book and the original results will be shredded. On the work book the results will assigned to the child's study code.		
What is the format of the key?	 Electronic		
Who will have access to the key?	Research Coordinators and Investigators		
Where will the key be stored and how will it be protected?	Location(s): All research data will be kept separately from the Master Key of coded, identifiable PHI/PII in an electronic database, which will be encrypted, double password protected and the access will be restricted. At the conclusion of the study, the research data will be de-identified prior to review and analysis. Confidentiality measures: The research data will be coded to mask the identity of the child. The code will be retained until the conclusion of the research study. Once a Final Report has been approved by the IRB, all the paper records will be stored and destroyed in accordance with the Long Term Storage Plan. The anonymized research data will not be utilized for further research activity beyond the protocol stipulations without additional IRB approval. At the end of all data mergers, or no later than at the closure of the study, all identifiable patient information will be destroyed based on AFI 33-332, "The Air Force Privacy and Civil Liberties Program" and the National Institute of Standards and Technology Special Publication (NIST SP 800-88) for the approved methods to destroy PII.		
Source of Research Material per Participant (Procedures)	# Routine Care	# Research Driven	# Total Procedures
Urine specimen	1	0	1
Participant Data Sheet completed by research staff	0	1	1
Satisfaction survey (Parent)	0	1	1
"All specimens kept at 99MDG will be handled and disposed of in accordance with federal regulations."			
g. Instrumentation: N/A			

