The alternatives for QW urine collection are urine specimen collection by using the bag specimen collection method or the invasive straight catheterization or suprapubic aspiration. The alternative to using an iodine cleansing solution is to use a normal saline solution. The parents also have the authority to deny their child's participation in the study.

6. DATA ANALYSIS**Data Analysis:**

Primary analysis will be performed by intent-to-treat including all randomized children, where primary outcome data are available, consistent with the CONSORT guidelines for intention to treat analysis. The primary outcome measure is a binary yes/no outcome of detection of microbial markers to determine level of contamination. The absolute difference between the two groups will be reported so that the percentage of contamination samples, together with the 95% CI for the differences of percentages, and calculate p values using a chi squared test. A p value of <0.05 will be considered significant. For the secondary outcome there will also be a measure of binary yes/no outcome of voiding urine within 5 minutes. The rate of successful voiding within 5 min will be described for each group with percentages and 95% CI. The p value will be estimated using chi squared test for categorical variables and t-test or Wilcoxon's rank sum tests for continuous variables.

Additionally we will also be evaluating patient's gender, and age in months for comparative data analysis to help strengthen the study's statistical design outcomes.

Outcome Measures:

Level of urine contamination (binary yes or no), if there was a sample collected in 5 minutes (binary yes or no), and time to void with a 300 second cap are the two outcome measures being evaluated in this study.

Sample Size Estimation/Power Analysis:

This is a pilot study and will have a relatively low sample of 60 subjects.

Statistical Analysis:

Data analysis will be conducted by Baylor University statistics department ([name])

Number of Subjects:	# Planned to Enroll	# Enrolled	# Planned to Complete Study	TOTAL
----------------------------	----------------------------	-------------------	------------------------------------	--------------

Number of Subjects at 99 MDG	60	0	60	60
------------------------------	----	---	----	----

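### Sections 3 and 3.e contradict each other on a child with a past iodine reaction: one places the child in saline without regard to the envelope, the other excludes (minor)

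*Combined protocol and SAP*

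**What the plan says.** Section 3 (Research Design and Methods) limits the offer of participation to children "meeting the inclusion/exclusion criteria will be offered an opportunity to participate". It describes allocation as follows: "Utilizing sequentially numbered opaque sealed envelopes (SNOSE), children will be randomly assigned to one of the two treatment groups".

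The same section has parents asked about any earlier allergic reaction to iodine, "prior to being placed in experimental group", and adds that "if they have had a reaction in the past they will be placed in the normal saline group instead". No product or form of iodine is named in that question.

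The exclusion criteria in section 3.e list "Children with past hypersensitivity reactions to iodine swabs". No other iodine history is listed there.

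Section 6 (Data Analysis) states: "Primary analysis will be performed by intent-to-treat including all randomized children", with the qualifier "where primary outcome data are available". It has no rule for a child whose arm was set by history.

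**The concern.** In a randomised comparison only the allocation sequence should decide the arm. The redirect lets a patient characteristic decide it, and in one direction only, since such a child can go to saline but never to iodine. It also sits beside an exclusion criterion that would keep at least some of the same children out of the study. Two members of staff, each following a different part of section 3, would enrol different children.

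What is at stake is mainly the integrity of the allocation rule and the clarity of the analysis set. A child placed in saline by history has no obvious status in section 6. The records may not show it either. The study code in section 3.f begins with A or B according to group, and the index card in the envelope carries both the group and the child's ID. The plan does not say which envelope, card or letter a redirected child receives.

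**Working it through.** The plan gives no iodine-reaction rate, so there is no stated figure to reproduce. The check compares the rules and then illustrates how large the effect could be.

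**Step 1: the two rules side by side**

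| Child's history | Section 3.e | Redirect in section 3 | Outcome |
|---|---|---|---|
| No iodine reaction | Eligible | Does not apply | Envelope decides |
| Past reaction to an iodine swab | Excluded | Enrolled, saline | Contradiction |
| Past reaction to another iodine product only | Eligible, if *iodine* is meant more widely than *iodine swabs* | Saline | History decides |

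The second row holds on any reading of the words. The third depends on the two terms differing in meaning.

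**Step 2: timing of the question**

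The wording "prior to being placed in experimental group" fits two sequences.

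- Before the envelope is opened: the child joins saline without being randomised. Section 6 covers randomised children and does not say whether this child is analysed.
- After an iodine card is drawn: the child was randomised to iodine but is cleansed with saline. Intent-to-treat counts the child as iodine. This is crossover, not selection bias.

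**Step 3: illustration of size**

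Inputs from the documents: 60 children (section 6); a 31% five-minute success rate and 27% contamination from earlier work (section 2). Assumptions: equal allocation, 30 per arm (the ratio is not stated); a share *p* of children with a past iodine reaction, taken as 0.1% to 5%; and, to get an upper bound, that the section 3.e exclusion is not applied.

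| *p* (assumed) | Children affected if asked before the envelope, 60*p* | Chance of at least one such child, 1 − (1 − *p*)^60 | Chance of at least one such sample, 1 − (1 − 0.31*p*)^60 | Crossovers if asked after an iodine draw, 30*p* |
|---|---|---|---|---|
| 0.1% | 0.06 | 6% | 1.8% | 0.03 |
| 0.5% | 0.3 | 26% | 8.9% | 0.15 |
| 1% | 0.6 | 45% | 17.0% | 0.3 |
| 5% | 3.0 | 95% | 60.8% | 1.5 |

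*Question after an iodine draw.* The intent-to-treat difference is (1 − *p*) times the true effect, so the effect is diluted by 0.1% to 5% of its own size.

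*Question before the envelope, child analysed as saline.* Redirected children form 60*p* / (60*p* + 30(1 − *p*)) = 2*p*/(1 + *p*) of the saline arm. Suppose contamination after saline differed by 20 points between children with and without the history; this is an assumed gap between those two kinds of child, not a treatment effect. The bias is then 20 × 2*p*/(1 + *p*) points:

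- *p* = 0.1%: 0.04 points
- *p* = 0.5%: 0.20 points
- *p* = 1%: 0.40 points
- *p* = 5%: 1.90 points

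*Yardstick.* With 27% contamination in both arms, the half-width of the 95% confidence interval is 1.96 × √(2 × 0.27 × 0.73 / *n*).

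- *n* = 30 × 0.31 = 9.3 samples per arm: 40.4 points
- *n* = 30 samples per arm, if every child yields one: about 22.5 points

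Even the largest illustrated bias is small beside either figure.

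**The case against.** The strongest reply is that this is loose drafting with no practical effect. Several parts of it stand.

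- **Wording.** The plan uses its iodine terms interchangeably. Section 2 speaks of povidone iodine swabs, section 3 of povidone iodine solution and of iodine swabs, and a reaction during the procedure is to iodine in section 3 but to the swab under Risks in section 4. A reader might infer that there is a definite group of eligible children, reactors to other iodine products, who are assigned by history. The documents do not establish that, because the two terms may mean the same thing. The contradiction for swab reactors remains either way.
- **Order of steps.** Because only eligible children are offered participation, a known swab reactor should be screened out first, leaving the redirect as a late safety check. That is a sensible reading, but the plan does not state this order.
- **Unseen material.** Section 12 lists a flow chart and a Participant Data Sheet that are not shown. Either might settle the timing or record a redirect.
- **Consequence.** A reader might infer that the control arm, and so the primary result, is biased. The documents do not support this. Nothing in them links a history of iodine reaction to contamination after saline, and section 6 restricts the analysis to randomised children, with a crossover counted as iodine. The reaction rates and the 20-point gap used above are assumptions, and the trial describes itself as a pilot.

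None of this reconciles the two instructions, and no other section does so.

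**Conclusion.** Wrong as written, and minor. For a child with a past iodine-swab reaction, the plan says both to exclude the child and to enrol the child in saline; under the second rule the envelope does not decide the treatment. This finding rests on the text alone and is secure.

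Whether a further group of eligible children is also affected depends on how widely *iodine* was meant, and that cannot be settled from the documents. Nor can the number of children: it is unknown, and the figures above show only what assumed rates would imply. The effect on the primary comparison is probably near zero and may be exactly zero. The reason to act is that the rule is incorrect and easily put right, not that it threatens the conclusion.

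**What to change.** 1. Delete the redirect sentence in section 3.
2. Ask every parent about any past allergic reaction to iodine at eligibility screening, before an envelope is opened.
3. Widen the exclusion in section 3.e from iodine swabs to any past allergic reaction to iodine.

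The third change is needed with the first: deleting the redirect alone would let a child who had reacted to another iodine product be randomised to iodine. With all three in place, every enrolled child is randomised, no child with a reported iodine reaction is exposed, and the analysis rule in section 6 needs no change on this account.

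The cost is one deleted sentence, a question moved to screening and one edited line. Perhaps a few children would be excluded, and they can be replaced to keep 60. The result would not apply to iodine-allergic infants, who could not receive iodine in any case.

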Parent consent will be acquired via the written consent forms prior to the initiation of any research activities.

Benefits:

There may be decreased levels of urine contamination in either the saline or the iodine prep group's urine sample. If so, this will give a child's treatment team more reliable test results and decrease the need for more invasive urine testing. Additionally the normal saline preparation may be effective at decreasing the level of contamination as the iodine, this is the benefit of using normal saline for a preparation and comparing it to the iodine.

Risks:

Procedure is safe and the only possible negative outcome could be skin irritation from the iodine prep group. There are risks that urine sample may show that there was growth of bacteria on culture in which event the parents will be contacted by the PI or AI and made aware of these results and will be advised to follow up with their pediatrician. There is a possibility that the child has an allergic reaction to the iodine swab. If this occurs, the child will be referred to their pediatric PCM. The urine sample collected during the QW procedure will still be used for the study. There may be a risk of inadvertent breach of confidentiality.

Costs: None

Safeguards for Protecting Information:

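### After an iodine reaction, one section discards the child's urine and data and another keeps the sample; the discard rule can remove children from the iodine arm only

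*Combined protocol and SAP*

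**What the plan says.** Three statements bear on a child who reacts to iodine.

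- **Section 3, Research Design and Methods.** "if the patient develops a reaction to iodine during testing then they will have the region cleansed with normal saline"; staff then evaluate the child, and the urine and the subject's "data will be disposed of and excluded from the study".
- **Section 4, Risks.** "There is a possibility that the child has an allergic reaction to the iodine swab". The child is then referred to the paediatric primary care manager, and "The urine sample collected during the QW procedure will still be used for the study". The same paragraph describes the procedure as safe and says that "the only possible negative outcome could be skin irritation from the iodine prep group".
- **Section 6, Data Analysis.** "Primary analysis will be performed by intent-to-treat including all randomized children, where primary outcome data are available". It does not mention an exclusion for reactions.

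Section 3 assigns povidone iodine to the experimental group and cold saline to the control group; only the experimental envelopes hold iodine swabs. On the secondary outcome, section 3 says: "If the child voids within five minutes the time in seconds will be recorded on the provided worksheet". The exclusion criteria list "Children with past hypersensitivity reactions to iodine swabs".

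**The concern.** A sample cannot be both thrown away and used. Two staff members working from different sections would build different analysis sets from the same children. It is also unclear whether the reaction meant in section 3 includes the skin irritation named in section 4.

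The section 3 rule carries a second problem. A control child treated as assigned is never exposed to iodine and so can never trigger it. The rule therefore removes children after randomisation, from one arm, because of an effect of the assigned treatment. If children who react differ from the others in contamination or voiding, the comparison is biased, and the direction cannot be known in advance. The trial is unblinded and the documents do not define a reaction, so the person deciding who is removed knows the arm.

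The rule discards the subject's data as well as the urine. That takes in the five-minute voiding result, and it may also take in the research record of the reaction itself. No section requires reactions to be reported by arm.

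**Working it through.** **1. Do the two rules cover the same event?** Section 3 is triggered by a reaction to iodine during testing, section 4 by an allergic reaction to the iodine swab. The sentence just before the section 3 rule speaks of an allergic reaction to iodine and then shortens it to a reaction, so the same event is meant. If section 3 is read more broadly, an allergic reaction during testing still falls under both rules.

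**2. Does the intent-to-treat wording allow the exclusion?** Section 6 limits the analysis to randomised children whose primary outcome is available. That covers a child who gives no sample. It does not cover a child whose sample was obtained, or could have been, and was discarded by rule. In that case the protocol creates the missing value. The source-material table in section 3 lists the urine specimen as routine care.

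**3. How large could the effect be?** The plan states no figure to reproduce. Inputs:

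- Total sample 60 (section 6). The allocation ratio is not stated; I assume 1:1, so n = 30 per arm.
- Five-minute success s = 0.31 and contamination c = 0.27, the earlier results quoted in section 2.
- Reaction rate r is not given; I show 1%, 5% and 10%. These are assumptions only.
- Success and contamination are taken as independent of reaction.

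Expected iodine samples: 30 × 0.31 = 9.3. One lost sample is 1/9.3 = 10.8% of these; one lost child is 1/30 = 3.3% of the arm.

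Iodine-arm contamination after one sample is lost, starting from 2/9 = 22.2%:

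- lost sample contaminated: 1/8 = 12.5% (down 9.7 points)
- lost sample not contaminated: 2/8 = 25.0% (up 2.8 points)

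If instead all 30 gave a sample and 8 were contaminated (26.7%), losing one gives 7/29 = 24.1% or 8/29 = 27.6%.

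Five-minute success after one child is lost, starting from 9/30 = 30.0%: 8/29 = 27.6% if the child had succeeded, 9/29 = 31.0% if not.

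Most reactors would give no sample (1 − 0.31 = 69%), and losing them leaves contamination unchanged. The share giving a contaminated sample is 0.31 × 0.27 = 0.0837.

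P(at least one sample lost) = 1 − (1 − 0.31r)^30

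P(at least one contaminated sample lost) = 1 − (1 − 0.0837r)^30

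| Assumed r | At least one sample lost | At least one contaminated sample lost |
|---|---|---|
| 1% | 8.9% | 2.5% |
| 5% | 37.4% | 11.8% |
| 10% | 61.1% | 22.3% |

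**The case against.** The strongest reply concerns size.

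- **The figures show sensitivity, not bias.** If reaction is independent of outcome, dropping a reactor changes nothing on average: (2/9)(1/8) + (7/9)(2/8) = 22.2% for contamination, and (9/30)(8/29) + (21/30)(9/29) = 30.0% for success. Bias needs a link between reaction and outcome, and the documents give no evidence of one. This stands. The figures show how far one discard can move a small arm, not an expected shift.
- **Reactions may be rare.** Exposure is one ten-second cleanse, the section 3 rule applies only during testing, and past hypersensitivity is an exclusion criterion. This also stands; the rates in the table are assumptions.
- **Other missing data are far larger.** At 31% success, about 21 of 30 children per arm have no contamination result anyway. That is true, but that loss can occur in either arm and is not a discard of results in hand.
- **The rules might differ by timing.** Section 3 could mean a reaction during testing and section 4 one noticed after collection. The text draws no such line, and section 4 sets no time limit, so the overlap remains.
- **Interrupted attempts.** Keeping reactors raises the question of how to count a stopped attempt. Section 3 already answers it: no sample within five minutes is documented as a failure.
- **Unseen attachments.** The Participant Data Sheet may already have a field for reactions. If so, that part of the fix is only a check.

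**Conclusion.** The concern holds. The conflict between sections 3 and 4 is explicit, and following section 3 as written gives an analysis set that contradicts the intent-to-treat statement in section 6. The exclusion can fall only on the iodine arm and is caused by the assigned treatment.

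Its numerical effect is unknown and may be nil: it depends on a reaction rate the documents do not give and on whether reaction is related to outcome. With 1:1 allocation and the success and contamination rates quoted in section 2, one discarded sample would move iodine-arm contamination by −9.7 or +2.8 points. Confidence is high on the contradiction and on the one-arm structure; no claim is made that a material bias will occur. It should be fixed before enrolment.

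**What to change.** Delete the clause in section 3 that disposes of and excludes the urine and data, so that data handling agrees with the Risks paragraph in section 4 and with section 6. State that:

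- every randomised child stays in the assigned arm;
- the contamination result is used if a sample was obtained, and no sample is recorded if not;
- the five-minute voiding result is kept;
- reactions, separated into skin irritation and allergic reaction, are recorded on the Participant Data Sheet (adding a field if it has none) and reported by arm.

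A sensitivity analysis omitting children who reacted is optional; it would address any worry that the extra saline cleansing affected the sample. The consent document and flow chart should be checked for either rule.

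The cost is a short protocol amendment and at most one field on the data sheet, with no extra patients or procedures. The change concerns data only and leaves the clinical management of a reaction as it is.
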